### **Propofol group**

Refer to Anesthesia Protocol Sheet for Anesthesiologist for specific instructions on preparation and administration of the following drugs. A crystalloid infusion will be started at a rate of 10 ml/kg/h, and 0.015mg/kg midazolam (maximum 2mg) and 1mcg/kg fentanyl (maximum 150mcg) will be administered intravenously. Patients will undergo anesthetic induction depending on whether they were randomized to the propofol or methohexitol groups. Patient randomized to the propofol group will receive lidocaine 1mg/kg and propofol up to 2.5mg/kg (*total initial dose*) of propofol. The exact volume of drug (rounded to the closest milliliter) will be drawn up in two divided doses, each half-dose placed in a separate 60mL syringe. The infusion tubing that will be connected to each of the two 60ml syringes and the infusion tubing will be primed with a separate volume of study drug (measured at 2.5ml total volume for all the tubing). This same volume of study drug will remain in the infusion tubing after the infusion is complete, and therefore does not need to be added to the calculated *total initial dose* of study drug. The rate of infusion programmed on each of two Medfusion 3500 pumps will be 900cc/h. Each 60cc syringe will be placed in one of the Medfusion 3500 pumps and will be connected to infusion tubing which will, in turn, be connected to a 2-way infusion tubing splitter terminating in a single length of tubing connected to the patient's bedside intravenous (IV) catheter. This will allow each pump to operate independently and simultaneously during anesthetic induction.

If no loss of eye lash reflex results following this dose of propofol, an additional 0.5mg/kg of propofol will be administered over 30 seconds by hand (ie. not utilizing the Medfusion pumps). Following loss of eye lash reflex, patients will be given 0.6mg/kg rocuronium and will be ventilated with a tidal volume of 6ml/kg using the ventilator, for standardization of protocol. 3 minutes following administration of rocuronium, patients will undergo oral endotracheal intubation using a glidescope with a maximum of 1 attempt by the attending anesthesiologist. Following confirmation of adequate endotracheal tube placement, 2% of sevoflurane will be initiated for anesthetic maintenance with a fresh gas flow of 2L/min. Mechanical ventilation parameters will be standardized at 6ml/kg (ideal body weight) tidal volume, respiratory rate of 12 breaths/min for an end-tidal carbon dioxide concentration of 35-40mm Hg. If the

aforementioned minute ventilation is inadequate, the respiratory rate will be adjusted accordingly.

### **Methohexitol group**

Refer to Anesthesia Protocol Sheet for Anesthesiologist for specific instructions on preparation and administration of the following drugs. A crystalloid infusion will be started at a rate of 10 ml/kg/h, and 0.015mg/kg midazolam (maximum 2mg) and 1mcg/kg fentanyl (maximum 150mcg) will be administered intravenously. Patients will undergo anesthetic induction depending on whether they were randomized to the propofol or methohexitol groups. Patient randomized to the methohexitol group will receive lidocaine 1mg/kg and methohexitol up to 1.5mg/kg (*total initial dose*) of methohexitol. The exact volume of drug (rounded to the closest milliliter) will be drawn up in two divided doses, each half-dose placed in a separate 60mL syringe. The infusion tubing that will be connected to each of the two 60ml syringes and the infusion tubing will be primed with a separate volume of study drug (measured at 2.5ml total volume for all the tubing). This same volume of study drug will remain in the infusion tubing after the infusion is complete, and therefore does not need to be added to the calculated *total initial dose* of study drug. The rate of infusion programmed on each of two Medfusion 3500 pumps will be 900cc/h. Each 60cc syringe will be placed in one of the Medfusion 3500 pumps and will be connected to infusion tubing which will, in turn, be connected to a 2-way infusion tubing splitter terminating in a single length of tubing connected to the patient's bedside intravenous (IV) catheter. This will allow each pump to operate independently and simultaneously during anesthetic induction.

If no loss of eye lash reflex results following this dose of methohexitol, an additional 0.5mg/kg of methohexitol will be administered over 30 seconds by hand (ie. not utilizing the Medfusion pumps). Following loss of eye lash reflex, patients will be given 0.6mg/kg rocuronium and will be ventilated with a tidal volume of 6ml/kg using the ventilator, for standardization of protocol. 3 minutes following administration of rocuronium, patients will undergo oral endotracheal intubation using a glidescope with a maximum of 1 attempt by the attending anesthesiologist. Following confirmation of adequate endotracheal tube placement, 2% of sevoflurane will be initiated for anesthetic maintenance with a fresh gas flow of 2L/min. Mechanical ventilation parameters will be standardized at 6ml/kg (ideal body weight) tidal volume, respiratory rate of 12 breaths/min for an end-tidal carbon dioxide concentration of 35-40mm Hg. If the aforementioned minute ventilation is inadequate, the respiratory rate will be adjusted accordingly.

### **Both groups**

Following induction in both groups, the blood pressure and heart rate will be measured every one minute for the first 15minutes following the administration of either propofol or methohexitol, and all hemodynamic parameters (systolic blood pressure, diastolic blood pressure, heart rate) will be recorded on the data collection sheet.

Hypotension will be defined as a systolic blood pressure of less than 85 mmHg or greater than 30% decrease in the mean systolic blood pressure (as determined above), whichever is greater. If the patient develops hypotension with a systolic blood pressure of less than 85mm Hg during the 15 minutes following induction of anesthesia, the treatment algorithm outlined below will be followed (Eyraud et al., 1999; Mets, 2013):

One dose of phenylephrine will be administered if heart rate is 60 bpm or above, whereas 5mg of ephedrine will be administered if heart rate is below 60 bpm. The blood pressure will be rechecked 1 minute following, and the process repeated once or twice if necessary. If the

patient is still hypotensive following 3 total doses of vasopressors (phenylephrine and/or ephedrine), they will be considered to be in refractory hypotension and 0.5 Units of vasopressin will be administered. The blood pressure will be rechecked 1 minute following administration of vasopressin. If systolic blood pressure is still less than 85 mmHg, an additional 0.5 Units of vasopressin will be repeated once or twice as needed. Persistent refractory hypotension despite the aforementioned vasopressors will be treated with 4 micrograms of intravenous norepinephrine. All hemodynamic parameters for 15min following anesthetic induction will be recorded by the attending anesthesiologist.

Following anesthetic induction in both study groups, blood samples will be collected (as described above) at 3, 5, 10 and 15 minutes following anesthesia induction. The blood samples will be processed by dedicated research technician as described below.

Blood samples will be kept on ice at 4°C until processing. Serum samples will be allowed to clot by being left undisturbed at room temperature for 30-60 minutes. The clot will be removed by centrifuging at 1600 x g for 10 minutes @ 4°C. The liquid component (serum) will be transferred into a clean polypropylene tube using a Pasteur pipette, aliquoted, and stored @ -70°C. The plasma samples will be centrifuged at 1,600 x g for 15 minutes at 4°C and the plasma transferred to a clean microcentrifuge tube. A protease inhibitor cocktail will be added to improve the stability of desired peptides. Plasma samples will be aliquoted based on needed assay volumes and stored in -70°C until processed for data collection.

Failure to adhere to this predetermined induction and anesthetic protocol will exclude the patient from further participation in the study.

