### 1.3 Secondary Study Endpoints

During the first 15 minutes following anesthetic induction:

- (1) The total number of doses of vasopressors (ephedrine, phenylephrine or vasopressin) administered
- (2) Duration of each hypotension episode
- (3) Refractory hypotension (defined as systolic blood pressure <85mm Hg following 3 doses of vasopressors)
- (4) Systolic blood pressure (at 1 minute intervals)
- (5) Diastolic blood pressure (at 1 minute intervals)
- (6) Heart rate (at 1 minute intervals)
- (7) Blood levels of AVP, All, Epi, NE (at 3, 5, 10 and 15 min)

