applied to the ipsilateral arm. An appropriately-sized blood pressure cuff shall be defined as a cuff whose bladder length is at least 80% of the arm circumference, and whose width covers 2/3 of the distance from the elbow to the shoulder. Blood samples, for baseline analysis of AVP, All, NE and Epi levels, will be collected from the IV as follows: A tourniquet will be applied proximal to the intravenous catheter, following which 3cc of blood will be removed first to clear the 'dead space' in the intravenous line and prevent erroneous blood sampling. This blood will be discarded. A further 10cc of blood will be collected in appropriately labeled tubes (5ml in serum red top vacutainers tubes and 5ml in vacutainers tubes containing EDTA) and kept on ice until processing by our research technician, as described below. Following collection of the blood sample, 5cc of normal saline will be used to flush the line and prevent blood from clotting the catheter. A second IV will also be established in the preoperative area under local anesthesia as described above to administer intravenous medications and fluids intraoperatively according to current anesthetic standards of care.

**Operating Room Procedures:** Subjects will be attached to standard ASA monitors including electrocardiogram and pulse oximetry and noninvasive blood pressure monitor. Baseline blood pressure will be determined by taking three automated successive non-invasive blood pressure measurements every 1-2 minutes, until the systolic blood pressure (SBP) measurements is consistent (difference of no more than 10% between readings) with the patient lying in supine position. The average SBP and accompanying heart rate (HR) of these three measurements will be recorded as mean baseline values.

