#### **7.2.3 Following sample collection from several patients**

At a later time, after samples have been collected from several study participants, serum samples will be processed to quantify Angiotensin II and plasma samples for Arginine Vasopressin, Epinephrine, and Norepinephrine using commercially available kits. Angiotensin II concentration will be determined using RayBiotech Human AngII EIA (EIA-AngII). Other markers will be measured using ELISA kits from Abnova; Arg8-Vasopressin ELISA (KA0301), Epinephrine ELISA (KA1882), and Norepinephrine (KA1891). Samples will be processed according to manufacturer's instructions.

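### Angiotensin II is assayed in serum that clots at room temperature for 30 to 60 minutes with no inhibitor step written, and handling time is neither fixed nor recorded

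*Combined protocol and SAP*

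**What the plan says.** All references are to the combined protocol and SAP.

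- **Collection (7.2.2, baseline sample).** Each draw is split into "5ml in serum red top vacutainers tubes and 5ml in vacutainers tubes containing EDTA". The post-induction draws follow the same method.
- **Holding (7.2.2, Both groups).** "Blood samples will be kept on ice at 4°C until processing". No maximum time is given.
- **Serum route (same place).** "Serum samples will be allowed to clot by being left undisturbed at room temperature for 30-60 minutes". The clot is then spun out at 4°C. "The liquid component (serum) will be transferred into a clean polypropylene tube using a Pasteur pipette, aliquoted, and stored @ -70°C". No inhibitor is mentioned.
- **Plasma route (same place).** "The plasma samples will be centrifuged at 1,600 x g for 15 minutes at 4°C and the plasma transferred to a clean microcentrifuge tube". The next sentence reads "A protease inhibitor cocktail will be added to improve the stability of desired peptides", and the one after it returns to aliquoting and freezing plasma.
- **Assay (7.2.3).** "serum samples will be processed to quantify Angiotensin II and plasma samples for Arginine Vasopressin, Epinephrine, and Norepinephrine".
- **Endpoint (1.3, item 7).** "Blood levels of AVP, All, Epi, NE (at 3, 5, 10 and 15 min", where the second marker is angiotensin II. It is also named in Specific Aim 2 (1.1).
- **Analysis (8.3).** Changes from baseline are compared by a linear mixed-effects model with arm, time, their interaction and the stratification factors. Potential confounders may be added later, but handling time is not named.

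**The concern.** Two of the four markers, angiotensin II and vasopressin, are peptides; epinephrine and norepinephrine are not. The protocol treats its peptides as needing stabilisation, yet as written the stabilising step belongs to the plasma route. Vasopressin therefore gets a cold spin and an inhibitor, while angiotensin II stands at room temperature for a period that may vary two-fold, with neither.

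At stake is the quality of the angiotensin II part of Specific Aim 2. If the concentration changes in the tube, part of the variation between samples reflects how long a tube stood rather than which induction drug was given. Nothing requires clotting time or draw-to-spin time to be held constant or written down, so the analysis could not adjust for it.

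**Working it through.** The plan gives no figure to reproduce. The check has a textual part and an illustration of size.

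**Step 1. The two peptides side by side, from 7.2.2 and 7.2.3**

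| | Angiotensin II | Vasopressin |
|---|---|---|
| Tube | Red-top serum | EDTA |
| Before processing | On ice, no time limit | On ice, no time limit |
| Room-temperature step | 30 to 60 min | None stated |
| Spin | 4°C, after clotting | 4°C |
| Inhibitor | None written | Written, by position in the text |
| Time fixed or recorded | No | No |

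**Step 2. Size of a within-protocol difference**

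Assumption: first-order net loss at room temperature with half-life h. The documents give no h, so a range is shown.

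- Fraction left after t minutes: f(t) = 0.5^(t/h).
- Ratio of two identical samples handled for 30 and 60 min: f(30)/f(60) = 2^(30/h).
- Added standard deviation on the natural-log scale if clotting time is uniform over 30 to 60 min: (ln 2 / h) × 30/√12.

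| h (min) | f(30) | f(60) | Ratio | Added log SD |
|---|---|---|---|---|
| 15 | 25% | 6% | 4.0 | 0.40 |
| 30 | 50% | 25% | 2.0 | 0.20 |
| 60 | 71% | 50% | 1.41 | 0.10 |
| 120 | 84% | 71% | 1.19 | 0.05 |
| 240 | 92% | 84% | 1.09 | 0.025 |

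If the log SD between samples were otherwise 0.5 (a further assumption), the variance would be multiplied by 1 + (added SD/0.5)². That is 1.64, 1.16, 1.04, 1.01 and 1.00 for the five half-lives. With an SD of 0.3 the range is 2.78 to 1.01; with 0.8 it is 1.25 to 1.00.

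**Step 3. What this does to the planned comparison**

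- *Same handling time for every tube.* Every value is multiplied by the same f. Raw levels and raw differences between arms shrink by f, while log-scale changes are untouched. This is a level shift.
- *Handling time varies at random.* This adds noise, of the size in the last column of the Step 2 table.
- *Baseline tubes wait longer than later ones.* Baseline is drawn in the preoperative area and the others 3 to 15 minutes after induction, so different waits are possible. With no true change, a 60-minute baseline against a 30-minute later sample would show an apparent rise equal to the ratio column. This distorts change over time. If the pattern is the same in both arms, it does not by itself create a difference between them.
- *Handling time differs by arm.* Only this would bias the arm comparison, and nothing in the text suggests it.

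**The case against.** The strongest reply is that neither the size nor the direction of the effect is known. The documents give no rate of loss, and net formation in the tube would act the other way. The 4-fold figure needs the shortest half-life shown and two tubes at opposite ends of the window; at 240 minutes the effect is close to negligible. This stands, and it limits the point to a plausible weakness of unknown size.

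The inhibitor sentence names no tube. Its position points to plasma, but its plural is odd when only one peptide is assayed there. Omission from serum is therefore the natural reading, not a proven one. The ambiguity itself needs correcting.

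Section 7.2.3 also defers to the manufacturer's instructions, and the kit may call for serum. That reference sits under the later assay work and does not alter the written clotting step, but it does mean that a move to plasma must depend on the kit.

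A reader might infer more than the documents support:

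- **Bias between arms.** Both arms follow the same workflow, handled by a dedicated technician, and no section suggests different handling times by arm.
- **A spurious ACEI-versus-ARB difference.** No such comparison is planned. Drug type is a stratification factor (7.4.3) and a covariate (8.3), and the documents describe no mechanism by which in-tube change would differ between the two classes.
- **A conflict between ice and room temperature.** The text reads naturally as a sequence: ice first, then clotting as the start of processing. What remains is the missing time limit on ice.
- **Loss beyond repair.** EDTA plasma is drawn at every time point and frozen, and with consent specimens may be kept for up to 7 years (21.1 to 21.3). If volume and kit allow, that plasma might still be assayed.

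**Conclusion.** The point holds as a mismatch between the protocol's premise and its procedure. Peptides are said to benefit from stabilisation, but angiotensin II is assigned to the tube with a variable room-temperature period and no written inhibitor step. Following the plan exactly would probably give a noisier and level-shifted measure, with possible distortion of change from baseline.

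The figures, a 4-fold to 1.09-fold difference between permitted handling times and an added log SD of 0.40 to 0.025, rest entirely on assumed first-order net loss with half-lives of 15 to 240 minutes. The true effect could be small.

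The scope is one of four markers in Specific Aim 2 and secondary endpoint 7. The other three markers and the primary hypotension endpoint are not affected. The change is worth making because it is cheap, not because harm to the arm comparison has been shown.

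**What to change.** Revise 7.2.2 and 7.2.3 together.

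1. Check whether the named angiotensin II kit accepts EDTA plasma containing the inhibitor.
2. **If it does:** assay angiotensin II in cold EDTA plasma. Replace the 5 ml red-top tube with a second 5 ml EDTA tube, so that the draw stays at 5 + 5 = 10 ml. Add the inhibitor at collection, set a maximum draw-to-spin time, and drop the clotting step for this marker.
3. **If it requires serum:** state whether and when inhibitor is added to that tube, and set one fixed clotting time for all samples, baseline included. Record draw-to-spin time and use it in a sensitivity analysis of the 8.3 model.
4. **In either case:** name the tube that the inhibitor sentence refers to.

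The cost is one kit check, a tube change under the first option, and revised wording. No extra blood or patients are needed. Any samples already stored as serum should be reported separately from those collected under the revised procedure.

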#### **7.2.3 Following sample collection from several patients**

At a later time, after samples have been collected from several study participants, serum samples will be processed to quantify Angiotensin II and plasma samples for Arginine Vasopressin, Epinephrine, and Norepinephrine using commercially available kits. Angiotensin II concentration will be determined using RayBiotech Human AngII EIA (EIA-AngII). Other markers will be measured using ELISA kits from Abnova; Arg8-Vasopressin ELISA (KA0301), Epinephrine ELISA (KA1882), and Norepinephrine (KA1891). Samples will be processed according to manufacturer's instructions.

### **7.3 Duration of Participation**

The individual will only be participating in the study from the immediate preoperative period (after intravenous access has been established in the preoperative area) until 15 minutes following intubation. Standard anesthetic care will be provided to the individual by the attending anesthesiologist and primary provider in the room following this time, independent of study participation. There is no long-term follow-up involved for this study.

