## **3.3 Early Withdrawal of Subjects**

### **3.3.1 Criteria for removal from study**

1. Unanticipated difficult airway
2. Unanticipated arrhythmia occurring during or immediately following anesthetic induction
3. Unanticipated adverse effect of pre-induction drugs (lidocaine, fentanyl) or induction drugs (methohexitol or propofol).

4. Non-adherence to study protocol guidelines for practical reasons or safety reasons

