### **3.3.2 Follow-up for withdrawn subjects**

Not applicable

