### **11.0 Risks**

The research requires the establishment of a second intravenous line following anesthetic induction. The use of an additional intravenous line is common anesthetic practice, although (as with any invasive procedure) there is the risk of bleeding, infection at the venipuncture site and infiltration of the intravenous catheter with the infusion of medications or fluids. In this study, the line will be used to draw blood samples, but following termination of the study protocol it will be used for the administration of standard fluids and drugs required for anesthetic care.

While there is currently no evidence to suggest that either randomization arm is harmful compared to the other, there is the risk that patients will be randomized to receive an induction drug that may potentially cause more hypotension compared to the other. We will perform interim analysis of our data and stop the study should we have reason to believe that one medication is causing significant harm compared to the other. Patients will be randomized to receive either propofol or methohexitol which both have the potential to cause hypotension.

Risks of propofol:

>10% incidence: low blood pressure (3%-26%), Injection site burning, stinging, or pain (18%), stop breathing for 30-60 seconds (adults 24%)

1% to 10% incidence: abnormal heart rhythm (1% to 3%), slow or fast heart rate (1% to 3%), cardiac output (volume of blood pumped by the heart per minute) decreased (1% to 3%);

Risks of methohexitol (frequency not defined but these complications are considered very rare since methohexitol is considered standard of care):

Sudden stop in blood circulation due to the failure of the heart, low blood pressure, shutdown of arteries and veins in the arms and legs, fast heart rate, agitation coming out of general anesthesia, headache, anxiety, restlessness, seizures, convulsion, injection site pain, abdominal pain, nausea or vomiting, blood clot in your leg that blocks one or more of your veins, breathing problems (stop breathing, bronchospasm, cough, labored breathing, hiccups, spasm of the vocal cords making it difficult to speak or breath, inadequate breathing).

One of three trained anesthesiologists will be administering each of these induction drugs, and has the expertise to anticipate and effectively treat each of these potential complications.

There is a possible risk of loss of confidentiality of health information.

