### **12.2 Potential Benefits to Others**

The results of this study will be used determine whether methohexitol is a safer drug to use in anesthetic induction of patients receiving ACEI or ARBs (by causing less hypotension and less administration of vasopressor drugs). If this is the case, it may contribute to changing standard anesthetic practice and improving patient safety.

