## 19.2 Recording of Adverse Events

All adverse events (serious or non-serious) and abnormal test findings observed or reported to study team believed to be associated with the study drug(s) or device(s) will be followed until the event (or its sequelae) or the abnormal test finding resolves or stabilizes at a level acceptable to the investigator.

An abnormal test finding will be classified as an adverse event if one or more of the following criteria are met:

- The test finding is accompanied by clinical symptoms
- The test finding necessitates additional diagnostic evaluation(s) or medical/surgical intervention; including significant additional concomitant drug treatment or other therapy

**NOTE:** Simply repeating a test finding, in the absence of any of the other listed criteria, does not constitute an adverse event.

- The test finding leads to a change in study drug dosing or discontinuation of subject participation in the clinical research study
- The test finding is considered an adverse event by the investigator.

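### No adverse-event check is scheduled later than 15 minutes after intubation, and the entry on withdrawn patients does not fit the adverse-event section

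*Combined protocol and SAP*

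**What the plan says.** Section 7.3 describes participation as running from the preoperative period, "after intravenous access has been established in the preoperative area) until 15 minutes following intubation". Care after that point is ordinary anaesthetic care outside the study, and the section adds: "There is no long-term follow-up involved for this study".

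Section 11.0 lists the risks of each drug. The methohexitol list includes "agitation coming out of general anesthesia, headache, anxiety, restlessness, seizures, convulsion, injection site pain, abdominal pain, nausea or vomiting, blood clot in your leg".

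Section 3.3.1 names reasons for removing a patient from the study. One is "Unanticipated arrhythmia occurring during or immediately following anesthetic induction"; another is an unanticipated adverse effect of a pre-induction or induction drug. The whole entry in Section 3.3.2, on follow-up of withdrawn subjects, is "Not applicable".

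Section 19.2 takes in adverse events that the study team observes or hears of and believes to be drug-associated. It says that these "will be followed until the event (or its sequelae) or the abnormal test finding resolves or stabilizes at a level acceptable to the investigator". Section 10.3 has such events entered on a case report form and sent to the principal investigator within 24 hours. Neither section gives a date or time after which recording stops.

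**The concern.** When participation ends, the patient is intubated, has received a muscle relaxant and is on sevoflurane. A patient in that state cannot report headache or nausea and cannot show emergence agitation. The protocol warns of these effects but assigns nobody to look for them once they could appear. What is recorded then depends on who happens to notice an event, whether it is passed on, and whether a clinician who knows the allocation attributes it to the drug.

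For withdrawn patients the sections pull in different directions. An arrhythmia or an adverse drug effect is itself a ground for withdrawal, so the patients with the most relevant safety information are those for whom Section 3.3.2 plans nothing.

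The stake is the completeness of the safety record. Section 11.0 undertakes to stop the study if one drug appears to be causing significant harm relative to the other. Section 10.2 bases the interim analysis on haemodynamic and vasopressor data, so late harm would have to enter that judgement through the passive route.

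**Working it through.** The plan states no figure on this point, so there is none to reproduce. The check is a timing argument, a count and a short calculation of what 60 patients per arm can show.

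**1. When scheduled observation ends.** In both arms rocuronium follows loss of the eyelash reflex, and then "3 minutes following administration of rocuronium, patients will undergo oral endotracheal intubation". Adding the 15 minutes of Section 7.3 gives 3 + 15 = 18 minutes after rocuronium. This covers the 15-minute haemodynamic window, which starts at induction. I assume that it falls before emergence, since these are elective operations under maintained general anaesthesia.

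**2. Methohexitol risks in Section 11.0.** With the breathing problems taken as one entry there are 15: cardiac arrest, low blood pressure, peripheral vascular shutdown, fast heart rate, emergence agitation, headache, anxiety, restlessness, seizures, convulsion, injection-site pain, abdominal pain, nausea or vomiting, leg clot, breathing problems.

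Seven would normally show only at or after emergence: emergence agitation, headache, anxiety, restlessness, abdominal pain, nausea or vomiting, leg clot. This classification is mine. The result depends on the counting rule:

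- Plain count: 7/15 = 47%.
- The seven breathing problems counted singly, so 15 − 1 + 7 = 21 items: 7/21 = 33%.
- Seizures and convulsion added because a muscle relaxant can mask them: 9/15 = 60%, or 9/21 = 43%.

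The range is 33% to 60%.

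**3. Propofol risks in Section 11.0.** There are six: low blood pressure, injection-site pain, apnoea, abnormal rhythm, slow or fast heart rate, reduced cardiac output. None is late by timing: 0/6. However, this list contains only effects in the bands above 10% and from 1% to 10%. The methohexitol list has no frequencies, and its entries are called very rare. The two counts therefore follow different rules and cannot be compared as rates.

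**4. Withdrawn patients, section against section.** Section 3.3.1 removes a patient for an arrhythmia or drug effect. Section 3.3.2 plans no follow-up. Section 19.2 requires follow-up of drug-associated events to resolution or stability and does not exempt withdrawn patients. Section 8.1 allows for drop-out of up to 20%, that is 0.20 × 120 = 24 patients for all reasons together. The documents do not say how many of these would be withdrawn for an adverse event.

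**5. What complete follow-up of 60 per arm could show.** The chance of at least one case in an arm is 1 − (1 − p)^60. The values of p are illustrative, because the documents give no late-event rates.

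- p = 0.1%: 1 − 0.999^60 = 5.8%.
- p = 1%: 1 − 0.99^60 = 45%.
- p = 3%: 1 − 0.97^60 = 84%.

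If no case is seen in 60, the one-sided 95% upper limit is 1 − 0.05^(1/60) = 4.9%. Longer observation would describe common late effects but could not compare very rare ones between arms.

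**The case against.** The strongest reply is that Section 7.3 sets the length of participation and does not close adverse-event recording. Sections 10.3 and 19.2 have no cut-off, and Section 19.5 requires reporting of unexpected, probably related harms to the ethics board without a time limit. One of three trained study anaesthesiologists is assigned to the case (Section 7.2.1), and nothing says that this person leaves before emergence. This stands. Late events are not invisible to the study; they are not actively sought.

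Section 3.3.2 can also be read as concerning outcome follow-up only, with Section 19.2 governing adverse events. That reading is possible, but the text does not state it, and a coordinator reading Section 3.3.2 alone would stop.

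A reader might infer from 7 of 15 against 0 of 6 that the window flatters methohexitol. The documents do not support this. The lists follow different rules, no late-event rate is given for either drug, the window is the same in both arms, and no between-arm adverse-event analysis is planned (none in Section 8.3; Section 10.7 plans no tests).

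A reader might also take Section 12.2, which says that the trial will "determine whether methohexitol is a safer drug to use in anesthetic induction of patients receiving ACEI or ARBs", as a general safety claim. The same sentence defines the term by less hypotension and less vasopressor use, both measured inside the window.

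**Conclusion.** The point holds as a gap in safety ascertainment and a conflict between sections. No adverse-event check is scheduled beyond 15 minutes after intubation. About half of the named methohexitol risks (7 of 15; 33% to 60% by counting rule) therefore depend on passive, open-label reporting filtered by a causality judgement. Sections 3.3.2 and 7.3 must be reconciled with Sections 10.3 and 19.2 for patients withdrawn because of an adverse event.

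The size rests on my classification of which listed effects appear late, and on the assumption that scheduled observation ends before emergence. The direction and size of any effect on an arm comparison are unknown. The primary endpoint and the listed secondary endpoints lie within 15 minutes of induction and are unaffected. The change is worth making because it is cheap, but it would not turn the trial into a comparison of rare harms.

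**What to change.** - **Section 7.3:** keep the 15-minute haemodynamic window. Add a safety window in which the existing research coordinator abstracts adverse events from the medical record through recovery-room discharge, and serious events through hospital discharge, in the same way in both arms.
- **Section 3.3.2:** replace the present entry with the same safety window for withdrawn patients, and refer to Section 19.2 for events still open when it closes.
- **Sections 10.3 and 19.2:** refer to this window, so that the period of active collection is stated once and consistently.
- **Section 8.3:** add a descriptive table of adverse events by randomized arm, without a test, because 60 per arm cannot compare very rare events.

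Section 12.2 needs no change.

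The cost is a short chart review for 120 patients and matching consent wording; no visit or procedure is added. Postoperative events unrelated to the induction drug will be recorded as background in both arms.
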